High Flow Nasal Cannula (HFNC): Nasal cannula system that delivers flow rates of respiratory gas meeting or exceeding a patient's normal spontaneous inspiratory flow demand. HFNC systems must maintain adequate heating and humidification of the delivered gas to protect the airway tissues from dryness.

High Velocity Nasal Insufflation (HVNI): The use of HFNC with specified parameters including flow rates, fraction of oxygen, gas temperature and cannula interface dimensions to achieve a defined therapeutic effect.

Non-Invasive Positive Pressure Ventilation (NIPPV): Breathing assist where a mask is strapped tightly to a patient's face and bi-level pressure is administered at an established frequency to support a patient's minute ventilation.

Mechanical Ventilation (MV): Breathing assist that requires intubation and the delivery of forced positive pressure breaths at a set frequency.

Respiratory Failure: The inability to maintain sufficient arterial blood oxygen saturation and CO₂ levels during unassisted spontaneous breathing.

Pulmonary Rehabilitation: Exercise regimen for patients with compromised cardio-pulmonary function.

Vapotherm Transfer Unit (VTU): system composed of a roll stand, power source and gas supply that allows the Precision Flow to function independently of wall connections and therefore become mobile, facilitating therapy during ambulation.

Ambulatory Oxygen: A portable oxygen cylinder device allowing the patient to carry around their oxygen supply so as to breathe during routine mobility & exercises.

Pulse Oximetry Reading (SpO₂): Indirect measure of a patient's arterial blood oxygen saturation using pulse oximetry technology.

Resting SpO₂: SpO₂ value the patient demonstrated at rest, while sitting upright and connected to the patient monitors prior to the start of the study session. This value will be patient specific and reflect the patient's clinical status.

Desaturation SpO₂: The SpO₂ value considered to be the point of desaturation. This value is based on the desaturation requirement for reimbursement of oxygen therapy.

Ventilatory Work Effort / Work of Breathing (WOB): The physical, physiologic muscular demands of breathing manifested through the sign and symptoms of increased physical exertion, which include airway resistance, use of accessory muscles for inspiration or expiration.

Fraction of inspired oxygen (FiO₂; %): The percent of the delivered respiratory gas mixture that is oxygen, expressed as a fraction.

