These **endpoints** will establish the effect HVNI therapy may have on improving patient ambulation relative to TAU, while potentially demonstrating the effect of HVNI on hospital resource allocation and patient comfort.

Vapotherm, Inc

HVNI Ambulation Feasibility Study

Confidential

III. Subject Selection

Subjects will be identified and recruited by study investigators. The feasibility study will take place at a clinical setting (e.g. hospital, academic center, out-patient facility), where testing can be performed with appropriate supervision and staff training to maintain patient safety. The test model is a modified 6MWT. Initial contact will be made by the study investigators, and the participants may or may not decide to enroll. Compensation will be provided to participants for enrollment into this study.

Inclusion Criteria

1. Adults over the age of 18 years
2. Demonstrated respiratory distress upon mild to moderate exertion (e.g. dyspnea upon standing, walking, etc.)
3. Candidate for clinical ambulation/mobilization
4. GOLD 4 spirometry or GOLD 3 with significant dyspnea on exertion with or without supplemental oxygen

Exclusion Criteria

1. Hypoxemia at resting baseline with $SpO_2 < 88\%$ with supplemental oxygen
2. Inability to provide informed consent
3. Pregnancy
4. Known contraindication to perform ambulation, per site SOC practices
5. Inadequate respiratory drive or any known contraindications to HVNI
6. Inability to use nasal cannula and HVNI therapy
7. Agitation or uncooperativeness
8. Determined by the attending clinician to be sufficiently unstable or unsuitable for this feasibility study

IV. Study Design

The study objective is to evaluate the ability of HVNI to improve patient ambulation relative to TAU by using a modified 6MWT model. The hypothesis is that HVNI therapy, when implemented in conjunction to ambulatory practices, will be more effective than TAU to improve patient by reducing the patient's perceived dyspnea and exertion via maintaining oxygenation (reduced desaturation) and supporting ventilation (reduced WOB).

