Baseline Characterization Sitting down, the subject will be setup and prepared for the ambulation test with appropriate data recording devices and supplemental oxygen (not HVNI). The subject will be allowed to acclimate to the supplemental oxygen during this period of time. While subject is at rest, standing up, the following data will be collected (see Table 1): RR, HR, BP, SpO₂, and RPD (Modified Borg scale 0-10). For the RPD & RPE, the coordinator will record patient scores, the FiO₂ and flow settings for any supplemental oxygen provided to the patient before/during/after this baseline phase. TAU will not include HVNI in this study period. The Ambulation Test will be performed after the baseline characterization is. The definition for this ambulation test will be to walk until 18 minutes has elapsed or the patient is unable to continue. A timer will keep track of the test duration, and the clinician will keep track of the distance traveled during ambulation. At test start, test end, & 1-minute intervals the subjects will be asked to rate their RPE (Modified Borg scale 0-10). The subject vitals will be monitored during this ambulation test and recorded as follows: HR, RR, SpO₂. The ambulation test will end if the subject has completed 18 minutes, stops walking for more than 10 seconds, has to sit down, has any adverse events, or should the investigator deem necessary.

Recovery Interval will begin immediately following the end of the Ambulation Test. The subject will perform this recovery interval while safely seated. The time to return to the subject's resting-while-standing RPD score (Baseline) will be used as recovery time. At the end of the recovery interval, record the subject RR, HR, BP, SpO₂, and RPD & RPE. Any adverse events will be recorded. Any exacerbations from ambulation walk test will be recorded during the recovery interval. Record the recovery end time and date.

After the Recovery Interval is complete, all associated data will be collected including clinician perception/satisfaction scores. Then the study will pause until the next ambulation test is scheduled. The next ambulation test will be determined per standard practice and when deemed appropriate by the investigator.

Test Session

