All other pharmaceutical and medical treatment will remain the purview of the attending physician and will be administered per the current standards. This study is designed to evaluate only intervention of HVNI in conjunction with standard (TAU) ambulatory practice, and it is assumed that the ancillary interventions will

Vapotherm, Inc
HVNI Ambulation Feasibility Study
Confidential

follow common clinical practice guidelines and conventions. All treatments given to the subjects will be noted on their CRFs.

VapoTherm, Inc
HVNI Ambulation Feasibility Study
Confidential

VII. Data Collection

Table 1. Key study data and collection points.

	Baseline Characterization	Ambulation Test	Recovery Interval	@ Study End
Patient History & Health	X			X
Treatment: Flow & O2	X	X	X	X
Physiologic Parameters	X	X	X	X
Performance Parameters		X		
Recovery Parameters			X	
Clinician Perception Scores			X	X
Disposition	X			X

Patient enrollment data collection will include patient history, health, demographics, and interventions. For each test session the following data will be recorded for comparison.

Physiologic Parameters

- SpO₂, HR, RR, BP, RPE, RPD

Performance Parameters

- Test duration and test distance traveled

Recovery Parameters

- Return time to baseline RPD, HR, RR, BP, SpO₂, RPD, RPE

Primary Endpoint

- Distance and duration of exercise during ambulation

Secondary Endpoints

- Physiologic parameters – SpO₂, HR, RR, BP, RPE, RPD
- Recovery parameters: return time to baseline Rated Perceived Dyspnea score
- Modified Borg scale scores – Rated Perceived Exertion (RPE), Rated Perceived Dyspnea (RPD)

Tertiary Endpoints

- Clinician perception of patient respiratory response to therapy, ranging from NO Response to Excellent Response, as continuous VAS.
- Clinician perception of frequency of rain-out, interface slippage or other technical/clinical difficulties applying therapy, ranging from Never to Frequent as continuous VAS.
- Clinician perception of patient comfort and tolerance of therapy, ranging from Very Poorly Tolerated to Very Well Tolerated as continuous VAS.

Vapotherm, Inc

HVNI Ambulation Feasibility Study

Confidential

- Clinician perception of Simplicity of set-up and use, ranging from Complex to Setup and Use to Simple to Setup and Use, as continuous VAS.
- Clinician perception of Monitoring and support of therapy required (adjustments, refilling fluids, adjusting interface), ranging from Almost Constantly to Almost Never, as continuous VAS.

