VIII. Statistical Analysis

The data analysis will be “per protocol.” Baseline patient demographics and characteristics will be summarized, and appropriate statistical testing will be performed for the continuous and categorical variables. Assuming a non-normal data distribution for this crossover study design, the non-parametric Wilcoxon Signed Rank Sum test will be performed with significance interval of 0.05 on all applicable variables. Otherwise, for the categorical variables, the Fisher’s Exact test will be performed. Data will be compared and graphed accordingly for a visual comparison with accompanied statistical notations.

IX. Risks and Discomforts

This pilot study does not present significant risk to patients, as supplemental oxygen is routinely provided to patients and the 6MWT is a standard/routine practice³³. The Treatment-as-Usual at the study sites involves the application of simple supplemental oxygen during mobilization. Use of the high flow nasal cannula therapy has no known risks and has been used in the clinical setting for approximately seventeen years without known reports of adverse events related to the administration of high nasal flows when appropriately conditioned to near body temperature and fully humidified. The literature indicates that approximately only 4 cmH₂O of distending pressure may be generated in the upper airway^{34,35} which is well below any known threshold for injury. In addition, it has been demonstrated that delivery of high flows of conditioned gas from a nasal cannula has a positive effect on airway mucosal function^{36,37}. The patients will be closely monitored as part of standard medical practice. Ambulation is implemented as part of the standard care practice for the patients included in this study.

For these reasons, we have determined that this study represents non-significant risk to the subjects, beyond the discomfort related to routine ambulation therapy.

X. Potential Benefits

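### Recovery time is scored while seated but against a standing dyspnea baseline, so it can partly measure the act of sitting down; separately, exclusion 1 does not say in which posture resting SpO₂ is read.

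*Combined protocol and SAP*

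**What the plan says.** Three places in the protocol fix a posture, and one leaves it open.

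- **Definitions at the front of the protocol.** Resting SpO₂ is the "SpO₂ value the patient demonstrated at rest, while sitting upright", on the monitors and before the session begins.
- **Section VI, Baseline Characterization, Control and Test Sessions.** The subject is set up and instrumented sitting, but then: "While subject is at rest, standing up, the following data will be collected". The list is RR, HR, BP, SpO₂ and RPD on the modified Borg scale.
- **Section VI, Recovery Interval, both sessions.** "The subject will perform this recovery interval while safely seated". The endpoint rule follows: "The time to return to the subject's resting-while-standing RPD score (Baseline) will be used as recovery time".
- **Section III, exclusion 1.** It begins "Hypoxemia at resting baseline with" and sets the limit at SpO₂ below 88% on supplemental oxygen. It states no posture.

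Section VII lists among the secondary endpoints "Recovery parameters: return time to baseline Rated Perceived Dyspnea score". Section VIII says that "the non-parametric Wilcoxon Signed Rank Sum test will be performed with significance interval of 0.05 on all applicable variables", so recovery time will be compared within patient between TAU and HVNI.

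**The concern.** Recovery time should measure how long the subject takes to get over the walk. Here the score is taken in one posture and the target in another. Inclusion criterion 2 gives breathlessness on standing as an example of the distress that qualifies a subject, so in this population sitting down may itself lower RPD. Part of the measured recovery could then be the change of posture, and a subject whose RPD rose little during the walk could reach the target almost at once.

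What is at stake is the interpretation of the recovery endpoint, which Aim 2 names first among the secondary outcomes. Section V says that the study's data will inform the sample size of a follow-on randomized study, so the measure may be carried forward.

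A smaller matter of wording goes with it. A site applying exclusion 1 may take the seated value that the definitions describe or the standing value that the baseline procedure collects.

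**Working it through.** The documents give no figure for a posture effect or for recovery time, so there is nothing of the plan's own to reproduce. The check is a comparison of the texts, followed by an illustration on assumed values.

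**Step 1. Postures side by side**

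| Item | TAU session | HVNI session |
|---|---|---|
| Set-up and instrumentation | sitting | sitting |
| Baseline RPD and vital signs | standing | standing |
| Recovery interval | seated | seated |
| Recovery target | standing RPD | standing RPD |

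The mismatch is within each session. Between sessions the rule is identical.

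**Step 2. Effect on each recovery time.** Assume that seated dyspnea decays exponentially toward its seated resting level: RPD(t) = S + (P - S)·exp(-kt), where S is seated rest, P is the score at the end of the walk and k is the rate. Let the standing target be S + p, where p is the standing-sitting gap. Setting RPD(t) = S + p gives

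T = (1/k)·ln[(P - S)/p].

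A larger p shortens T. Assumed values: k = 0.5 per min, S = 1, P = 6 on TAU and 5 on HVNI.

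| p (Borg points) | TAU: 2·ln(5/p), min | HVNI: 2·ln(4/p), min | Difference, min |
|---|---|---|---|
| 0.25 | 5.99 | 5.55 | 0.45 |
| 0.5 | 4.61 | 4.16 | 0.45 |
| 1 | 3.22 | 2.77 | 0.45 |
| 2 | 1.83 | 1.39 | 0.45 |

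Each time falls by more than half as p goes from 0.5 to 2. The difference does not move, because p cancels: 2·ln(5/p) - 2·ln(4/p) = 2·ln(5/4) = 0.45. Linear decay at a common rate r behaves in the same way: T = (P - S - p)/r, and p/r cancels.

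**Step 3. When the contrast does move**

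- *The gap differs by therapy.* With p = 1 on TAU and 0.5 on HVNI: 2·ln(5/1) - 2·ln(4/0.5) = 3.22 - 4.16 = -0.94 min. With p = 0.5 on TAU and 1 on HVNI: 4.61 - 2.77 = +1.83 min (from unrounded values).
- *The recovery rate differs by therapy.* With the same rise of 5 points in both sessions, k = 0.5 on TAU and 0.7 on HVNI, the difference is (1/0.5 - 1/0.7)·ln(5/p) = 0.571·ln(5/p). This is 1.71, 1.32 and 0.92 min at p = 0.25, 0.5 and 1. Here an equal gap does compress the difference.

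**Step 4. Exclusion 1.** At enrollment, Section VI lists demographics, anthropometrics and history, but no SpO₂. The first SpO₂ in the procedures, and the first data column of Table 1, is Baseline Characterization, which is standing. So the seated value in the definitions has no scheduled collection point, and the value that is scheduled does not match the definition. For scale, assume whole-number readings and a lower standing value. With a 1-point drop, a seated 88% reads 87% standing and eligibility changes, while a seated 89% reads 88% and stays eligible. With a 2-point drop, both 88% and 89% change.

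**The case against.** The standing target is written out explicitly and identically in both sessions, so it looks deliberate, and the within-patient comparison is like for like in posture. That stands. A reader might infer that the mismatch must shrink any HVNI-TAU difference even when it affects both sessions equally. Step 2 shows otherwise: under a common rate of recovery an equal gap cancels. Compression or bias needs something that differs by therapy. The protocol's hypothesis, that HVNI lowers perceived dyspnea, makes such a difference plausible but does not show it.

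A reader might also infer that HR, RR, BP and SpO₂ must return to standing values before recovery ends. Section VI defines recovery time by RPD alone; the others are only recorded at the end of the interval. The Recovery Parameters line in Section VII is loosely punctuated, but it names RPD a second time, which suggests a list of recorded items. Section VIII specifies no test of recovery vital signs against baseline.

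On exclusion 1, it is fair to say that the only definition of a resting SpO₂ is a sitting one, so the criterion can be read as having a single posture. It leaves the posture unstated rather than mixing two. Nor do the documents support saying that a subject could begin walking below a protocol limit: exclusion 1 is an enrollment criterion, no SpO₂ threshold for starting the walk is set, and the decision to ambulate rests with the research team.

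Finally, a seated reference has its own hazards. The target may be lower and harder to reach; in the formula above, T grows without bound as p approaches 0. The protocol gives no maximum recovery time and no rule for a subject who does not return to baseline. The timing also matters. In the TAU session acclimation happens during Baseline Characterization; in the HVNI session titration and acclimation come before it. A reading taken simply at set-up could fall at different stages in the two sessions.

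**Conclusion.** The concern holds in a limited form. In both sessions a seated score is timed against a standing target, so recovery time can partly measure posture. This assumes that dyspnea is higher standing than sitting. Inclusion criterion 2 makes that reasonable here, but the documents do not quantify it.

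Bias in the HVNI-TAU contrast is possible but not established: it requires a standing-sitting gap or a rate of recovery that differs by therapy. The illustration shows that either could matter (from -0.94 to +1.83 min around 0.45 min for unequal gaps), but every input to it is assumed and it estimates nothing about this trial. No figure in the plan changes. Recovery time is secondary, and the primary endpoint of walking distance and duration does not use the recovery target. This is a cheap improvement to a named endpoint, not a flaw in the main comparison.

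The exclusion 1 point is one of wording: the definition, the criterion and the baseline procedure do not agree on a posture and must be reconciled.

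**What to change.** 1. **Seated reference.** In both sessions, record RPD, SpO₂, HR, RR and BP once while the subject is seated and instrumented, after acclimation to that session's oxygen therapy and just before standing. State this timing in the same words for both sessions. Use the seated RPD as the target for the seated recovery time.
2. **Keep the standing reading** as the walk-start value, and keep recovery time to the standing target as a sensitivity measure. Comparing the two also shows the size of the posture gap in each session, which is the unknown here.
3. **Non-return.** Because some subjects may take longer to reach the seated target or not reach it, state how such a subject enters the signed-rank comparison.
4. **Exclusion 1.** Reconcile the definition of resting SpO₂, exclusion 1 in Section III, and the Baseline Characterization text for both sessions in Section VI, so that the criterion names one posture and that reading has a scheduled collection point. The choice of posture belongs to the clinical lead.

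The cost is one extra set of readings per session, taken while the subject is already sitting and fitted with the recording devices, added fields on the case report form, and a wording change. The drawback is a possibly lower target, which items 2 and 3 address.

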Ambulatory care oxygen denotes the use of supplemental oxygen during any form of mobility, exercise, and daily life activities⁷. Use of ambulatory oxygen in patients with respiratory distress has become prevalent as patients often desaturate (hypoxemic, <88%) during exercise & mobility assessments^{7,8,14}. This desaturation, especially in patients with resting hypoxemia challenges, has been associated with reduced exercise tolerance, reduced FEV₁, and in chronic cases even increased patient mortality^{10,11,13}. It is also used by patients on long-term oxygen treatment during any exercise¹⁵. In fact, pulmonary rehabilitation has become a standard of care (SOC) for patients with respiratory diseases, with evidence supporting the benefits of exercise to improved dyspneic, quality of life (QOL) outcomes, hospital resource allocation, psychosocial benefits, and cost-effectiveness⁸. The long-term benefits of using oxygen, in conjunction to ambulation, is still debated¹⁶⁻¹⁸. Clear episodic improvements have been demonstrated to improve exercise performance measures^{7,8}, reduce exercise dyspnea¹, improve recovery time^{8,19}, reduce WOB⁸, reduce incidence of cardiopulmonary complications²⁰, and in some cases improve patient mental health^{8,14}. Systematic reviews have also highlighted the correlation between longer hospital stays and greater chances for complications followed by lengthened rehabilitation due to muscle wasting, which may be ameliorated through early ambulation^{7,8}. A study in COPD patients even suggested that a 4% desaturation during 6-minute-walk-tests (6MWT) may predict long-term mortality¹¹.

Multiple studies have demonstrated improved activity, performance, reduced dyspnea, and improved SpO₂ saturation as positive patient outcomes of ambulation during MV and non-invasive ventilation (NIV). In fact, early ambulation of patients requiring MV has been communicated as clinically useful as early as 1975²¹. Previously, NIV has been shown to increase exercise tolerance, reduce exercise desaturation episodes, and thereby improve pulmonary rehabilitation^{8,22}. Menadue et al. specifically explored NIV's effect on exercise in acute hypercapnic exacerbations of respiratory disease, and demonstrated that oxygen by NIV improved the

Vapotherm, Inc

HVNI Ambulation Feasibility Study

Confidential

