As Vapotherm Hi-VNI technology becomes more common-place in hospital standard of care & practice, HVNI therapy may also have a demonstrable effect on improving patient ambulation and mobility. Mobility represents a key factor in the timely improvement of patient health, and in end-of-life cases it can have a mental impact⁸. In addition to the patient benefits, ambulation and early ambulation & mobility can also reduce the patient hospital resource allocation and reduce the length of stay (LOS). Some hospitals have included patient ambulation metrics as a key success factor, and this also can play a role to stepping-down

Vapotherm, Inc

HVNI Ambulation Feasibility Study

Confidential

the patients to less critical care environments. The goal of this study is to establish a low risk model, modified from the 6MWT, for patients with dyspnea: (1) evaluate the effect of HVNI on ambulation, and (2) assess the impact HVNI use may have on improved outcomes when compared to standard TAU (HVNI).

Vapotherm, Inc
HVNI Ambulation Feasibility Study
Confidential

II. Overall Study Objective

The **overall objective** of this study is to evaluate the ability of HVNI to improve patient ambulation relative to a treatment as usual (TAU).

The **hypothesis** is that HVNI therapy, when implemented in conjunction to ambulatory practices, will be more effective than TAU to improve patient mobility by reducing the patient's perceived dyspnea and exertion via maintaining oxygenation (reduced desaturation) and supporting ventilation (reduced work of breathing [WOB]).

To test this hypothesis, the study will be conducted with the following specific aims:

Aim #1: Primary Outcome. The primary endpoint is exercise performance, defined as the distance and duration of patient ambulation.

Aim #2: Secondary Outcomes. The secondary endpoints evaluate the patient recovery interval, defined as the recovery time (return time to baseline perceived dyspnea). Other endpoints will include: vital signs (heart rate [HR], respiratory rate [RR], blood pressure [BP]), arterial oxygen saturation (SpO₂), rated perceived exertion (RPE), and rated perceived dyspnea (RPD).

Aim #3: Tertiary Outcomes. The tertiary endpoints evaluate the clinician perception scores. For the clinician perceptions this will include: technical/clinical difficulties, patient comfort & tolerance, ease of use, monitoring & support for therapy, and expected/perceived patient outcomes.

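### SpO2, RPD and RPE are compared between walks of unequal, open-ended length with no time point, summary or SpO2 recording interval named, so the usual summaries can disfavour or hide an HVNI benefit

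*Combined protocol and SAP*

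**What the plan says.** - **Hypothesis (Sections II and IV).** HVNI is expected to improve mobility by lowering perceived dyspnea and exertion "via maintaining oxygenation (reduced desaturation" and by reducing work of breathing.
- **Desaturation (definitions list).** The entry reads "The SpO₂ value considered to be the point of desaturation", followed by "This value is based on the desaturation requirement for reimbursement of oxygen therapy". It gives no figure and no rule on duration or number of readings. Section I, as background, says that "patients often desaturate (hypoxemic, <88%) during exercise & mobility assessments". Section III uses 88% as a resting exclusion limit. Neither figure is linked to an endpoint.
- **Walk length (Section VI, both sessions).** Subjects are to "walk until 18 minutes has elapsed or the patient is unable to continue". The walk also ends if the subject pauses for more than 10 seconds, sits, has an adverse event, or is stopped by the investigator. Distance and duration form the primary endpoint (Section VII).
- **Recording during the walk (Section VI).** HR, RR and SpO2 are monitored and recorded, with no interval given. Borg ratings are scheduled at start, end and each minute. The Control session names RPE only; the Test session names RPD and RPE. Table 1 marks physiologic parameters for the ambulation phase without separating the sessions.
- **Endpoints and test (Sections VII and VIII).** The secondary list is "SpO₂, HR, RR, BP, RPE, RPD", plus recovery time and the Borg scores. All applicable variables go to a Wilcoxon signed-rank test at 0.05. No time point or summary is named.

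**The concern.** A signed-rank test needs one number per subject per session. For SpO2, RPD and RPE the plan does not say whether that number is the value at the end of the walk, the worst value, the average, or the value at a common minute. This would matter little if walks had a fixed length. Here length is itself an outcome, and it is expected to be greater on HVNI if the hypothesis is right. The end, worst and whole-walk summaries then compare different amounts of exercise. The definitions list describes Borg exertion ratings as made at equal workload, and those summaries do not meet that condition.

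The comparisons that speak to the proposed mechanism could therefore understate, hide or even reverse a real effect. With the summary left open, it could also be chosen after the data are seen. Section V says the study is to inform the size of a follow-on randomized study, so a misleading mechanism result could be carried forward. Same-minute SpO2 may be unrecoverable if it was not logged at fixed minutes.

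**Working it through.** **Plan figure.** The plan gives no figure for this comparison, so there is none to reproduce. Its calculated N of 26 (Section V) serves below as the number of pairs.

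**Simple case.** If SpO2 falls steadily, the shift in end or lowest SpO2 from extra walking alone is slope × extra minutes. With assumed slopes of 0.25 to 1 point per minute and 1 to 4 extra minutes, it runs from 0.25 × 1 = 0.25 to 1 × 4 = 4 points. If instead SpO2 levels off as fall × (1 − exp(−t/τ)), the end-value shift for a typical subject is fall × [exp(−T/τ) − exp(−(T + extra)/τ)]. With an assumed fall of 6 points, T = 7 min and 2 extra minutes:

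- τ = 3 min: 6 × (0.0970 − 0.0498) = 0.28 point
- τ = 1.5 min: 6 × (0.0094 − 0.0025) = 0.04 point

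The shape of the fall therefore matters as much as the extra time.

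**Simulation.** Assumptions, none from the documents:

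- start at 95%
- subject-level fall averaging 6 points (SD 40% of that); the steady case is 1 point per minute on average
- reading noise SD 1, values rounded to whole points, one reading per minute
- TAU walk averaging 7 min (SD 2.5)
- extra HVNI time with SD 1 min

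From the documents: 26 pairs, the 18-minute cap and the signed-rank test at 0.05 (taken as two-sided). There were 400 runs per scenario.

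No true oxygenation effect: mean difference HVNI − TAU in points, with the percentage of runs calling HVNI significantly worse.

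| SpO2 pattern | Extra min | End | Lowest | Whole-walk mean | Isotime |
|---|---|---|---|---|---|
| Steady fall | 2 | -2.03 (100%) | -2.05 (100%) | -1.02 (100%) | 0.00 (4%) |
| Steady fall | 4 | -4.03 (100%) | -4.02 (100%) | -2.00 (100%) | 0.02 (2%) |
| Levelling, τ = 3 | 2 | -0.34 (17%) | -0.55 (63%) | -0.44 (93%) | 0.01 (2%) |
| Levelling, τ = 3 | 4 | -0.59 (43%) | -0.95 (98%) | -0.79 (100%) | -0.03 (3%) |
| Early plateau, τ = 1.5 | 2 | -0.13 (6%) | -0.34 (34%) | -0.36 (81%) | 0.00 (4%) |
| Early plateau, τ = 1.5 | 4 | -0.15 (7%) | -0.55 (70%) | -0.59 (100%) | 0.03 (1%) |

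With equal walks every summary is within 0.05 of zero. The lowest value stays biased under a plateau because a longer walk gives more noisy readings from which to take a minimum. The whole-walk mean stays biased because more of a longer walk is spent at the plateau.

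True benefit, SpO2 fall 25% smaller on HVNI:

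| SpO2 pattern | Extra min | End | Lowest | Whole-walk mean | Isotime |
|---|---|---|---|---|---|
| Steady fall | 2 | +0.27 | +0.17 | +0.13 | +1.76 |
| Steady fall | 4 | -1.25 | -1.37 | -0.63 | +1.78 |
| Levelling, τ = 3 | 4 | +0.88 | +0.47 | +0.28 | +1.32 |

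A full reversal appears only with a steady fall and 4 extra minutes. With levelling off, the benefit shrinks but keeps its sign.

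**Borg scores.** No arithmetic applies. A subject who stops because of symptoms may report a similar score at the stop in both sessions even if the climb was slower on HVNI. Also, read literally, the Control session has no RPD rating between baseline and recovery, so neither end-of-walk nor same-minute RPD could be paired with the Test session.

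**The case against.** The strongest reply is that the plan is silent, not wrong. It does not commit to end, lowest or mean values, and RPE is already collected each minute in both sessions, so a same-minute RPE analysis remains open. That stands: a reader might infer that the plan penalises HVNI, but the documents show only that it could, depending on a summary not yet chosen and on whether SpO2 plateaus. For Borg scores the likely problem is masking, not a penalty, and no data in the documents show how far end scores converge. Walks can also end for reasons other than symptoms.

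A reader might also infer that the protocol has no desaturation threshold. It does cite <88% in Section I; what is missing is a link from that figure to the definition or an endpoint. Because the listed endpoint is SpO2, not desaturation, the missing cut-off breaks no planned test.

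The simulated sizes rest on assumed inputs, and the 4-point figure is the extreme of an assumed grid. Subjects who complete 18 minutes in both sessions have equal walks and no such bias. Isotime is not equal workload either: pace is not fixed, and a subject who walks faster on HVNI could still look worse at the same minute. These are secondary endpoints in a feasibility study.

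These points limit the size and certainty of the concern. They do not supply the missing time point, summary or recording interval.

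**Conclusion.** The point holds as an underspecified secondary analysis with a foreseeable direction of error. The documents establish that walk length is open-ended up to 18 minutes and is part of the primary endpoint, and that SpO2, RPD and RPE go to a paired test with no summary named. If end, lowest or whole-walk values are used, longer HVNI walks can lower the apparent SpO2 result. For 2 extra minutes and no true effect, the end-value shift ranges from about -0.1 point (early plateau) to -2.0 points (steady fall). Isotime stayed within 0.03 point of zero, under assumptions that ignore pace. All sizes are illustrative.

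A reader might go further and conclude that the main result is compromised, or that the mechanism results will contradict it. The documents support neither: distance and duration do not depend on these summaries, and reversal of a true benefit arose only in the most extreme of the assumed benefit scenarios. The change should be made, but the trial's primary comparison does not depend on it.

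**What to change.** 1. **Recording.** Log SpO2, HR and RR at the one-minute marks in both sessions. Reconcile the Control and Test descriptions in Section VI so that RPD as well as RPE is rated each minute in both.
2. **Main comparison.** In Section VIII, name isotime, the last full minute completed in both of a subject's walks, as the time point for SpO2, HR, RR, RPD and RPE. Add lowest SpO2 up to isotime. Keep end-of-walk values as supportive.
3. **Desaturation.** Tie the analysis definition to a stated number; Section I cites <88%. Report the proportion of one-minute readings below it up to isotime. Use time below the number only if continuous oximetry is stored, since one-minute readings cannot measure it well. This is an analysis definition only, not a rule for managing subjects.
4. **Pace.** Report distance covered by isotime if it is logged. Otherwise state that equal time does not guarantee equal workload.

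**Cost.** Analysis wording, a few case report form fields, and reading the monitor each minute; HR, RR and SpO2 are already monitored. The one added rating is RPD during the Control walk. Data after isotime become supportive only. The recording change has to be in place before the walks, because readings not logged at fixed minutes may not be recoverable.
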